After screening, subjects will receive the following tests: (1) Measurement of hepatic glucose production, substrate oxidation and plasma ketone/lactate/insulin/glucagon concentrations; (2) (Measurement of whole body norepinephrine turnover with ^3H -norepinephrine infusion; (3) Measurement of heart rate variability; (4) Measurement of liver fat content with ^1H -MRS; (5) 75-grams oral glucose tolerance test (OGTT)

The studies will be performed in a random order.

After the completion of the above studies, subjects in each group will be randomized (in 2:1 ratio) to receive for 12 weeks, empagliflozin 25 mg per day (n=24) or placebo (n=12), in a double blind fashion. The drug treatment will be started (day 1) on the day of the second hepatic glucose measurement (see specific details below). On day 2, the measurement of heart rate variability and norepinephrine turnover will be repeated. Subjects will continue treatment with the drug (empagliflozin or placebo) that they received during the second hepatic glucose measurement for 12 weeks and at the end of 12 weeks, all baseline tests will be repeated.

The treatment period could be extended based upon the circumstances until the repeat studies are completed.

Tests	Baseline	Day 1-3	12 Weeks
OGTT	OGTT		OGTT
HGP	Short	Long	Short
NE	NE	NE	NE
MRI	MRI		MRI
DEXA	DEXA		
HRV	HRV	HRV	HRV

The metabolic effects of empagliflozin lasted for 2 weeks in our previous studies (7). However, Ferrannini and colleagues (40) reported that at 4 weeks, the glucose effects of empagliflozin (HGP) are attenuated while the fat effects (fat oxidation and ketone production) are enhanced. Therefore, to evaluate the long term metabolic impact of SGLT2 inhibition, we decided to extend the treatment period in the current study to 12 weeks.

Specific Methods:

Screening: Medical history and physical examination will be performed. Blood samples will be drawn for CBC, blood chemistries, lipid profile, thyroid function and HbA1c. EKG will be performed.

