Boehringer Ingelheim Pharmaceuticals, Inc.

[name]

[contact]

For each adverse event, the investigator will provide the onset date, end date, intensity, treatment required, outcome, seriousness, and action taken with the investigational drug. The investigator will determine the expectedness of the investigational drug to the AEs as defined in the Listed Adverse Events section of the Boehringer Ingelheim's (BI's) Investigator Brochure for the Product BI Drug

Information e.g. Summary of Product Characteristics (SmPC) or Product Information (PI) for the authorised Study Drug provided by BI,

After the individual patient's end of trial: the investigator does not need to actively monitor the patient for new AEs but should only report any occurrence of cancer and trial treatment related SAEs which the investigator may become aware of by any means of communication.

Data Analysis Plan: Data Analysis and Statistical Plan: Glucosuria Induced Increase in Hepatic Glucose Production: Under steady-state postabsorptive conditions, the basal rate of endogenous (primarily reflecting hepatic) glucose appearance ($R_a = bHGP$) equals the ^3H -glucose infusion rate divided by steady state plasma ^3H -glucose specific activity. After drug (empagliflozin) administration, non-steady state conditions for ^3H -glucose specific activity prevail and the rate of whole body glucose appearance (R_a) is calculated from Steele's equation (52). The difference between HGP in empagliflozin-treated and placebo-treated subjects, in each group (i.e. NGT, IFG and T2DM), represents the increase in HGP stimulated by glucosuria.

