During the Oral-IV double tracer infusion study, only the ^{14}C -glucose which escapes the liver and non-hepatic splanchnic tissues appears in the systemic circulation, while all of the infused ^3H -glucose appears in the systemic circulation. Therefore, the difference between R_a calculated with ^3H -glucose and R_a calculated with ^{14}C -glucose represents the basal rate of hepatic plus non-hepatic splanchnic tissue glucose uptake. Thus, the basal rate of EGP will be calculated for ^3H -glucose as the ^3H -glucose infusion (dpm/min) divided by the steady-state plasma ^3H -glucose specific activity (dpm/mg). The rate of ^{14}C -glucose appearance will be calculated as the ^{14}C -glucose infusion rate (dpm/min) divided by the steady-state plasma ^{14}C -glucose specific activity (dpm/mg). The hepatic and non-hepatic splanchnic glucose uptake equals $R_{a3\text{H}-\text{glucose}}$ minus $R_{a^{14}\text{C}-\text{glucose}}$. Norepinephrine clearance rate will be calculated as ^3H -NE infusion rate (dpm/min) divided by the steady state plasma ^3H -NE radioactivity (dpm/ml) (between 12 and 20 min). Norepinephrine spill over (release) rate (pg/min), which reflects the sympathetic nervous system activity (53), will be calculated as the product of plasma norepinephrine concentration (pg/ml) and norepinephrine clearance rate (ml/min). The difference between norepinephrine spill over in empagliflozin-treated and placebo-treated subjects, in each group (i.e. NGT, IFG and T2DM), represents the effect of glucosuria on the sympathetic nervous system activity. The ratio between plasma ^3H -DHPG to ^3H -NE (between 20 to 120 minutes) will be used as an index of neuronal uptake of norepinephrine (54).

Values will be presented as mean \pm SD. Difference between means will be compared by ANOVA. Post hoc testing will be performed with the Bonferroni test.

The increase in HGP caused by glucosuria in each treatment group will be related to the change in norepinephrine spill over rate with Pearson's correlation in each treatment group. We anticipate a strong correlation between the two variables.

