We anticipate that empagliflozin will increase norepinephrine spill over to the plasma in T2DM patients as well, and that the increase in norepinephrine spillover will strongly correlate with the increase in HGP. Because the methodology utilized in the present study measures the rate of total body norepinephrine spill over, it is possible that the increase in epinephrine spill over from specific organs, e.g. kidney and splanchnic (primarily hepatic) tissue, will be diluted in the systemic circulation. Thus, it is possible that only a modest effect of empagliflozin on sympathetic activity will be detected. In such a scenario, measurement of organ specific (58), e.g. renal norepinephrine spill over (with renal vein catheterization) and splanchnic (with intraduodenal ³H-NE infusion and arterial or hepatic vein sampling) can be employed to quantitate the change in sympathetic activity in the kidney and liver.

Sample Size Calculation We powered the study to detect a significant increase in the basal rate of HGP following empagliflozin administration versus placebo. In previous studies, the increase in the rate of HGP versus placebo following empagliflozin administration was 0.34 ± 0.26 mg/kg.min. Therefore, we computed that 30 subjects in 2:1 randomization (20 empagliflozin and n=10 placebo) provide >90% power to detect a significant difference in HGP between empagliflozin-treated and placebo-treated subjects (in 3 groups comparison) at alpha <0.05. Therefore, to ensure 30 completers, we have set the sample size at 36 in each group.

Item 7 Risks Section:

Complete the following table to describe the risks of all **research procedures** listed in Step 2, Institutional Form (items 28-34). *Do not list risks of Routine care procedures here.*

X N/A, Risks are described in the informed consent document – do not complete this table.

Research procedures	Risks
example: 
• History and physical• Questionnaire• Laboratory tests	List the reasonably expected risks under the following categories as appropriate:
Add or delete rows as needed	
	

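### HGP is the outcome that the main study is powered on, but the plan does not fix the visit, post-dose window or group that decides, or the family for the Bonferroni test

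*Combined protocol and SAP*

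**What the plan says.** **Powered outcome.** Item 6, Sample Size Calculation (main study): "We powered the study to detect a significant increase in the basal rate of HGP following empagliflozin administration versus placebo". The planning effect is given as "following empagliflozin administration was 0.34 ± 0.26 mg/kg.min", and "we computed that 30 subjects in 2:1 randomization (20 empagliflozin and n=10 placebo) provide >90% power" ("in 3 groups comparison) at alpha <0.05"). Enrolment is then set: "to ensure 30 completers, we have set the sample size at 36 in each group". No visit is named.

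**Visits.** The test table in Item 6, Study Design, has HGP-Short at baseline, HGP-Long around the first dose and HGP-Short at 12 weeks. Specific Aims 1 and 2 (Item 4) instead give day 1 and 4 weeks. HGP-Long is sampled every 20-30 minutes for 5 hours after the dose.

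**Contrast and test.** Item 6, Data Analysis Plan: "The difference between HGP in empagliflozin-treated and placebo-treated subjects, in each group (i.e. NGT, IFG and T2DM), represents the increase in HGP" due to glucosuria. A parallel contrast is defined for norepinephrine (NE) spillover, measured at baseline, on day 2 and at 12 weeks. The test is stated once: "Difference between means will be compared by ANOVA. Post hoc testing will be performed with the Bonferroni test". The ANOVA factors and the comparisons that Bonferroni covers are not given.

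**Rank.** NE spillover has no power statement. The introduction to Sub-Study 2, however, describes sympathetic activation as what the study is mainly about.

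**The concern.** Two visits under randomised treatment can each yield the HGP difference, and the day 1 visit yields a whole curve. The plan's own rationale for 12 weeks of treatment cites a report that "at 4 weeks, the glucose effects of empagliflozin (HGP) are attenuated while the fat effects (fat oxidation and ketone production) are enhanced". The two visits could therefore give different answers. With no deciding visit or window named, the choice can be made after the data are seen, and the stated 0.05 then does not describe the chance of a false claim that empagliflozin raises HGP.

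Sub-Study 2 shows the contrast within the same protocol: it fixes its analysis window (390 to 420 minutes) and divides alpha by four in its sample size. The main study has nothing equivalent.

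**Working it through.** **Inputs.** From the main-study Sample Size Calculation: difference 0.34, spread 0.26 mg/kg.min, 20 versus 10 completers, 36 enrolled per group (24 versus 12), alpha 0.05. From the Data Analysis Plan: three groups. From Study Design: two HGP visits on treatment. Assumptions: 0.26 is an SD, tests are two-sided, effect and SD are the same in each group, groups are independent, and r is the within-subject correlation between the two visits' test statistics (no value is given in the documents).

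**1. The plan's own figure.** Standard error = 0.26 × √(1/20 + 1/10) = 0.1007. Noncentrality = 0.34 / 0.1007 = 3.376. With 28 df and critical t = 2.048, power is 90.3% (normal approximation 92.2%). The 2:1 size for 90% power is 10 placebo and 20 empagliflozin. The stated figure therefore reproduces for one contrast, in one group, at one visit, with no adjustment.

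**2. Power if Bonferroni covers the three groups.** Alpha per group = 0.05/3 = 0.0167.

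| Completers per group | Power (t test) |
|---|---|
| 30 (20 vs 10) | 79.0% |
| 36 (24 vs 12) | 87.4% |
| 39 (26 vs 13) | first size to reach 90% |

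Using the pooled error of a three-group ANOVA (84 df) gives 82.2% at 30 completers, so this does not restore 90% either.

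**3. False-claim rate over the two HGP visits, with Bonferroni over groups at each visit.** Let q be the chance of at least one false positive over the two visits in one group, each tested at 0.0167. The family-wise rate is 1 − (1 − q)³.

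| r | q | Family-wise rate |
|---|---|---|
| 0 | 0.0331 | 9.6% |
| 0.5 | 0.0313 | 9.1% |
| 0.8 | 0.0272 | 8.0% |
| 0.9 | 0.0245 | 7.2% |

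The choice of post-dose window is not counted here and would add to these figures.

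**4. Two groups instead of three.** Item 5 lists two main-study populations (type 2 diabetes, and FPG below 126 mg/dl). With two groups at 0.025 each and r = 0, the rate is 1 − 0.975⁴ = 9.6%, so the conclusion does not depend on the count of three.

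**5. Could the visits disagree?** If the week-12 effect were 25% or 50% smaller than planned (assumed), power for one unadjusted contrast at 30 completers would be 68.6% or 37.1%. A positive day 1 with a null week 12 would then be an ordinary outcome.

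**The case against.** Several points on the other side stand.

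- **Multiplicity is not ignored.** A reader might infer that there is no control at all and quote the rate for six unadjusted HGP tests (24.8% at r = 0.5). The documents do not support that, because a Bonferroni test is named. What is missing is its family. If it was meant to span both visits, the excess in step 3 disappears, but power falls further (70.1% at 0.05/6, t test, 30 completers).
- **HGP is implicitly first.** It is the only powered outcome, so HGP and NE spillover should not be read as interchangeable primaries. The planned mechanistic conclusion also needs HGP to rise, NE spillover to rise and the two to correlate. Under a global null at one visit, with r = 0.5 between the two and Bonferroni over groups, both are significant in some group with probability 3 × (2 × 0.0167 − 0.0313), about 0.6%. A rate that counts any one positive among twelve HGP and NE tests applies only if they are claimed separately.
- **The text leans to day 1.** The HGP-difference sentence follows the description of non-steady-state calculation with Steele's equation after dosing, which fits HGP-Long. But the sample size section speaks of the *basal* rate, which also fits week 12, and neither is named.
- **Attenuation is not certain.** The Background (Item 3) also reports the HGP rise persisting through treatment, including at 4 weeks, and Study Design gives week 12 a durability purpose. The visits may differ; the plan does not predict that they will.
- **The study is mechanistic,** so strict control over every group, visit and endpoint is partly a matter of judgement. It still states an alpha and a power, and these need a named test.

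**Conclusion.** The point holds in this form: the outcome is clear, but the deciding visit, post-dose window, group rule and Bonferroni family are not. If Bonferroni covers only the groups within a visit, the chance of a false HGP claim over both visits is about 9% (7.2% to 9.6%) against a stated 5%. This rests on independent groups and an assumed between-visit correlation of 0.9 to 0. Separate claims on NE spillover, whose rank is not stated, would raise it.

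A reader might infer that the power of more than 90% is an arithmetic error. It is not: it is correct for one unadjusted contrast. It does not describe a three-group comparison with Bonferroni, where it is 79.0% per group at 30 completers.

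**What to change.** In the Data Analysis Plan:

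1. Name one primary contrast. For example: empagliflozin minus placebo in the change in HGP from the pre-dose mean (−30 to 0 min) to a stated late post-dose window of HGP-Long. A window of 240-300 min is one option that uses samples already scheduled; the main study does not itself specify one. The sponsor may choose week 12 instead, but must name one visit.
2. State the group rule. Either test each group with Bonferroni over the groups, or use a fixed sequence starting from one named group.
3. Make early-visit NE spillover key secondary, tested only in a group where the primary is significant and at that group's alpha. Make the other HGP visit secondary (week 12 as durability) and all remaining outcomes exploratory.
4. State the ANOVA factors and the exact comparisons in the Bonferroni family.
5. Reconcile the aims (day 1 and 4 weeks) with the design (12 weeks), and the two populations in Item 5 with the three groups analysed.
6. Restate power to match: 79.0% per group at 30 completers (87.4% at 36) with Bonferroni over three groups, or 90.3% for the first test of a fixed sequence.

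**Cost.** Wording only, with no added visits, samples or participants. A result at the non-primary visit can no longer be presented as confirmatory. With Bonferroni over three groups, the stated power per group is lower unless completers rise to 39 per group.

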Official Study Title: Effect of Empagliflozin on Hepatic Glucose Metabolism: Role of Autonomic Nervous System

NCT number: NCT03193684

IRB Approval Date: 05.23.2020

Unique Protocol ID: HSC20170214H

Protocol Template Form

Item 1 UTHSCSA Tracking Number	HSC20170214H
-----------------------------------	--------------

Item 2 Abstract / Project Summary	Provide a succinct and accurate description of the proposed research. State the purpose/aims. Describe concisely the research design and methods for achieving the stated goals. This section should be understandable to all members of the IRB, scientific and non-scientific. DO NOT EXCEED THE SPACE PROVIDED.
--	--

Purpose/Objectives: To investigate the effect of empagliflozin, an SGLT2 inhibitor on hepatic glucose production and the role of autonomic nervous system in mediating the increase in hepatic glucose production in response glucosuria
 
Research Design/Plan: the role of autonomic nervous system in the increase in hepatic glucose production caused by empagliflozin will be examined with norepinephrine (NE) turnover in two protocols. The first protocol is cross sectional, in which 36 T2DM patients will receive hepatic glucose production (HGP) and NE turnover will be measured before and after empagliflozin or placebo administration. In protocol 2, diabetic and non-diabetic subjects will receive baseline HGP, NE turnover,) and liver fat measurement before at 2 days after the start and 12 weeks after empagliflozin or placebo treatment.
 
Methods: the following techniques will be employed (1) Measurement of hepatic glucose production with ^3H-glucose infusion, with and without glucose clamp, (2) substrate oxidation with indirect calorimetry and plasma ketone/lactate/insulin/glucagon concentrations; (3) Measurement of whole body norepinephrine turnover with ^3H-norepinephrine infusion; (4) Measurement of heart rate variability; (5) Measurement of liver fat content with ^1H-MRS
 
Clinical Relevance: The results of the present studies will help identify the mechanism responsible for the increase in HGP caused by empagliflozin and the increase in ketone production. The first action of the drug ameliorates its clinical efficacy while the second increases the risk of adverse events (ketoacidosis). Identifying the mechanisms underlying these actions will help developing therapeutic strategies which increase the drug clinical efficacy and mitigates its adverse events.
	
---	--

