In your recruitment plan, how many different populations of prospective subjects do you plan to target? Provide number: 2

Identify the criteria for **inclusion**:

Identify the criteria for **exclusion**:

e.g., a population can be individuals with type 2 diabetes controlled with diet and/or a population of healthy controls. Or a population can be individuals attending an education program, etc.
 
List each different population on a separate row and provide a short descriptive label: (e.g., normal-healthy, diabetics, parents, children, etc.)
 
To add rows use copy & paste
		
Type 2 diabetic subjects	1) FPG< 240 mg/dl 2) Age 18-70 years 3) eGFR>60 ml/min 4) weight stable ($\pm 4\text{Lb}$) in the preceding 3 months 5) Good general health	1) Use of an insulin or SGLT2 inhibitor medications affects glucose tolerance 2) Major organ disease 3) eGFR <60 ml/min 4) type 1 diabetes
Subjects with FPG<126 mg/dl	1) FPG<126 and 2-h PG <200 mg/dl 2) Age 18-70 years 3) eGFR>60 ml/min 4) weight stable ($\pm 4\text{Lb}$) in the preceding 3 months 5) Good general health	1) Use of medications that affect glucose tolerance 2) Major organ disease 3) eGFR <60 ml/min
Sub-Study: Type 2 diabetic	1) current diagnosis of Type 2 Diabetes 2) fasting plasma glucose concentration <300 mg/dl 3) Subjects must be drug naïve or on stable dose of metformin and/or sulfonylurea in the preceding 3 months 4) body weight has been stable (± 3 lbs) over the preceding three months 5) does not participate in an excessively heavy exercise 6) good general health as determined by physical exam, medical history, blood chemistries, CBC, TSH, urinalysis, and EKG	1) eGFR > 60 ml/min 2) hematocrit > 34%, 3) allergy to iodine 4) Major organ disease
Sub-Study: non-diabetic	1) No diagnosis of diabetes (FPG <126 mg/dl) 2) body weight has been stable (± 3 lbs) over the preceding three months 3) does not participate in an excessively heavy exercise 4) good general health as determined by physical exam, medical history, blood chemistries, CBC, TSH, urinalysis, and EKG	1) eGFR > 60 ml/min 2) hematocrit > 34%, 3) allergy to iodine 4) Major organ disease

Item 6

Research Plan / Description of the Research Methods *a. Provide a comprehensive narrative describing the research methods. Provide the plan for data analysis (include as applicable the sample size calculation).*

Step-by-Step Methods: Study Design:

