Data Analysis and Statistical Methods. Under steady-state postabsorptive conditions, the basal rate of endogenous glucose appearance ($R_a = bEGP$) equals $3\text{-}3\text{H}\text{-glucsoe}$ infusion rate divided by steady state plasma tritiated glucose specific activity. After drug administration, non-steady conditions for $3\text{-}3\text{H}\text{-glucose}$ specific activity prevail and the rate of whole body of glucose appearance (R_a) is calculated from the Steele equation. The difference in EGP during the last half hour of the study (390 to 420 minutes) between subjects receiving empagliflozin (Measurement II) vs placebo (Measurement I) represents the increase in EGP caused by empagliflozin. The difference in EGP between subjects receiving empagliflozin without volume repletion (Measurement II) versus with volume repletion (Measurement III) represents the role of intravascular volume depletion in the stimulation of EGP. The difference in the change in EPG between Measurement II and Measurement III will be compared to the difference between Measurement I and Measurement IV will be compared with ANOVA. Post hoc testing will be performed with Bonferroni correction for multiple comparisons.

The same statistical/analytical approach will be employed for the measurement of plasma FFA, and beta-OH-butyrate concentrations.

Sample Size Calculation. In previous studies, we demonstrated that the mean difference in EGP during the last hour of EGP measurement in empagliflozin-treated (Measurement II) and placebo-treated (Measurement I) subjects was $0.70 \pm 0.34 \text{ mg/kg}\cdot\text{min}$ (mean \pm SD) (3). To detect a 50% decrease in this difference at alpha <0.05 during the volume repletion study (Measurement III) with 90% power and alpha = 0.0125 ($=0.05/4$), we computed that 32 subjects are required. Therefore, to ensure 32 completers, we have set the sample size at 36.

Risks in Sub-Study 2:

Blood loss: blood loss in sub-study 2 will be 165 ml at each EGP measurement. Thus, the total blood loss will be 660 ml

Radiation: total amount of radiation in sub-study 2 will be 59.6 mrem (13.4 at each EGP measurement and 6 mrem at DEXA scan)

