Anticipated Results and Potential Problems: Based upon our preliminary results, we anticipate that empagliflozin will produce a large increase in HGP in NGT subjects which will maintain the FPG concentration at the fasting level. Further, because the FPG concentration does not change following empagliflozin administration, we anticipate that neither the fasting plasma insulin nor glucagon concentrations will be affected by empagliflozin. Likewise, we anticipate a large increase in HGP in IFG subjects with no significant change in the fasting glucagon to insulin ratio. We also anticipate a shift in substrate oxidation (i.e. decrease in glucose oxidation and increase in fat oxidation) in NGT and IFG subjects with no significant increase in plasma ketone concentration. These results will provide strong evidence against a significant role of the increase in plasma glucagon to insulin ratio in the increase in HGP and shift in fuel consumption from glucose to fat oxidation following SGLT2 administration. Further, we anticipate that SGLT2 inhibitors will alter autonomic balance and increase sympathetic nervous system activity in NGT and IFG subjects and that the increase in sympathetic nervous system activity will be, at least in part, responsible for the increase in HGP. Thus, we anticipate a strong correlation between the increase in sympathetic nervous system activity and the magnitude of increase in HGP in IFG and NGT subjects.

It will be of great interest to examine the effect of empagliflozin on plasma lactate concentration in NGT subjects. If, as anticipated, empagliflozin causes a robust increase in fat oxidation, decrease in glucose oxidation and increase in lactate concentration in NGT subjects, without a change in ketones, FPG, FFA, insulin, and glucagon concentrations, this will provide a strong evidence in support of a direct effect of the drug on mitochondrial substrate oxidation, independent of SGLT2 inhibition. In such a scenario, future studies with MRI spectroscopy and ¹³C-acetate infusion to quantitate hepatic TCA cycle activity (55,56) before and immediately after the administration of SGLT2 inhibitor in NGT subjects will provide direct evidence in support of an inhibitory effect of SGLT2 inhibitor on mitochondrial function independent of SGLT2 inhibition.

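### The main study's stated power of over 90% is that of one unadjusted comparison in one group; Bonferroni over three groups would lower it to about 79–84% (two-sided)

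*Combined protocol and SAP*

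**What the plan says.** Item 6, Sample Size Calculation (main study), takes an HGP increase over placebo of 0.34 ± 0.26 mg/kg.min from previous studies. It states that 30 subjects randomized 2:1 (20 and 10) "provide >90% power to detect a significant difference in HGP between empagliflozin-treated and placebo-treated subjects (in 3 groups comparison) at alpha <0.05". To allow for dropout, "we have set the sample size at 36 in each group". It does not say whether the test is one- or two-sided, and it gives no adjusted alpha.

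Item 6, Data Analysis Plan, defines the effect of interest group by group: "The difference between HGP in empagliflozin-treated and placebo-treated subjects, in each group (i.e. NGT, IFG and T2DM"), is taken as the rise in HGP due to glucosuria. The method is one general statement for all endpoints: "Difference between means will be compared by ANOVA. Post hoc testing will be performed with the Bonferroni test". Neither the number of comparisons nor the contrasts are given.

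The number of groups also varies. The abstract (Item 2) says "diabetic and non-diabetic subjects will receive baseline HGP", and Item 5 asks "how many different populations of prospective subjects do you plan to target? Provide number: 2". The analysis plan lists three.

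The Sub-Study 2 sample size, by contrast, is computed "with 90% power and alpha = 0.0125", shown there as 0.05/4.

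**The concern.** The analysis plan calls for an empagliflozin–placebo contrast in each of several groups and names Bonferroni as its only post hoc method. The power statement, which mentions three groups, uses alpha 0.05 with no division. If the contrasts are adjusted, the stated power is not that of the test to be run.

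Group-specific results carry the mechanistic argument. Under Anticipated Results, "we anticipate that empagliflozin will produce a large increase in HGP in NGT subjects", and the case against a glucagon/insulin explanation rests on seeing that rise where those hormones do not change. A reader faced with a non-significant group would take the chance of having missed a true effect of the assumed size to be under 10%. Under a three-contrast two-sided adjustment it would be 16–21%.

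**Working it through.** **Inputs.** From Item 6, Sample Size Calculation: difference 0.34 mg/kg.min; spread 0.26, unlabelled and read here as a common SD; 20 and 10 completers per group; alpha 0.05. From the Data Analysis Plan: three groups and Bonferroni. Two-sided testing is assumed first, because sidedness is not stated.

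**Standardised effect and noncentrality.**
- d = 0.34 / 0.26 = 1.308
- ncp = d × √(20 × 10 / 30) = 1.308 × 2.582 = 3.376

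**Power** is the probability that a noncentral t with this ncp exceeds the critical value for the chosen alpha. Three versions are shown: a t-test within the group (df 28); the pooled ANOVA error (df 84 for three groups × two arms, df 56 for two groups × two arms); and the normal approximation.

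**The plan's own figure.** By the normal approximation at two-sided 0.05, power = Φ(3.376 − 1.960) = Φ(1.416) = 92.2%. The within-group t-test gives 90.3% and the pooled error 91.6%. The stated figure is therefore confirmed for one comparison. On a two-sided test, 20:10 is also the smallest 2:1 size that reaches 90% by any of the three methods; 18:9 gives 86.8% by t-test. Read that way, the 30 completers contain no margin for further comparisons.

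**With Bonferroni, 20:10 completers per group.**

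| Family | Alpha per contrast | Sides | Within-group t | Pooled error | Normal |
|---|---|---|---|---|---|
| None | 0.05 | two | 90.3% | 91.6% | 92.2% |
| Two groups | 0.05/2 = 0.025 | two | 83.7% | 85.5% | 87.2% |
| Two groups | 0.025 | one | 90.3% | 91.3% | 92.2% |
| Three groups | 0.05/3 = 0.0167 | two | 79.0% | 82.2% | 83.7% |
| Three groups | 0.0167 | one | 86.6% | 88.5% | 89.4% |

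For example, three groups by the normal approximation: Φ(3.376 − 2.394) = Φ(0.982) = 83.7%.

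**Sensitivity at two-sided 0.0167.**
- SD 0.23 gives 89–92%; SD 0.28 gives 72–77%.
- If all 36 complete (24:12), power is 87.4% (t), 89.5% (pooled) or 90.4% (normal).

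**Other tests the plan could mean.** With the same effect in every group, the omnibus F test over the six cells has about 99.7% power, and a treatment effect pooled over the three groups (60 versus 30) has over 99.9%.

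**The case against.** The strongest reply is that the arithmetic is right and that the adjustment is the reader's inference. Several parts of it stand.

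- **The family is not written down.** The Bonferroni sentence names no endpoint or contrast and could refer to comparisons among NGT, IFG and T2DM. Subjects are randomized within each group, and whether separately randomized populations need a familywise correction is a matter of judgement. The explicit 0.05/4 in Sub-Study 2 can even be read as a sign that no division was intended in the main study. This stands, so the adjusted figures are conditional.
- **Sidedness is open.** The sample size paragraph speaks first of an increase and later of a difference. One-sided, a two-group family keeps power at 90–92%, and the claim that 20:10 has no margin fails, since 18:9 at one-sided 0.05 already gives 92.9% by t-test. This stands. Three groups at 20:10 still fall short one-sided.
- **ANOVA comes first.** The omnibus and pooled tests exceed 90%. That is true, but the Data Analysis Plan defines the effect within each group, and 30 is a single-group calculation.
- **Enrolment is 36 per group.** Full completion would bring three-group two-sided power to 87–90%. The plan's own power claim, however, rests on 30 completers.

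A reader might go further and infer that the parenthesis about three groups promises an adjustment that was then miscalculated, or that the trial is too small. The documents support neither. The parenthesis may simply mean in each of three groups, and 79–84% is not inadequate power.

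**Conclusion.** Wrong as written, but minor. The figure of over 90% is correct for one empagliflozin–placebo comparison within one group at unadjusted two-sided 0.05. It has not been carried through to the Bonferroni testing that the plan names, and the plan does not define what that testing covers.

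If Bonferroni covers the three within-group contrasts, the two-sided shortfall against 90% is about 6–11 percentage points per group; one-sided it is about 1–3. If it covers two groups, the shortfall is about 3–6 points two-sided and nil one-sided. It would be too strong to say that the stated power fails under every family or every test.

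These figures assume that 0.26 is an SD common to all groups (a reading that returns the plan's own 30), that the true difference is 0.34 in each group, and that 20 and 10 complete. They are powers for one group at a time, not for success in all three.

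**What to change.** In the statistics paragraph of the Data Analysis Plan, add the Bonferroni family and sidedness for HGP, for example: *The Bonferroni family for HGP is the three within-group empagliflozin–placebo contrasts (NGT, IFG, T2DM), each tested at two-sided 0.0167.*

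In the main-study Sample Size Calculation, label 0.26 as an SD if it is one, and replace the power claim to match: *With 20 empagliflozin and 10 placebo completers per group, a difference of 0.34 and a common SD of 0.26 mg/kg.min, power is over 90% for a single unadjusted two-sided 0.05 comparison within a group, and about 82% (79–84% by method) per group at the Bonferroni-adjusted two-sided 0.0167.*

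If two groups are to be analysed, as Items 2 and 5 suggest, give two-sided 0.025 and 84–87% instead. If the sponsor intends no adjustment across groups, or a one-sided test, the plan should say so and quote the corresponding figure from the table above.

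The cost is one added sentence and one replaced sentence. Sample size and design are unchanged; the only downside is a less favourable stated power.
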